376	5.	A history of pelvic radiation treatment.
377 378	6.	Having been previously treated with at least 100 mg TID of Elmiron ® or greater than 10 mg of hydroxyzine per day for greater than 12 consecutive weeks.
379	7.	Having had augmentation cystoplasty.
380	8.	Having had a cystectomy or cystolysis.
381 382	9.	Having had a neurectomy (i.e. hypogastric nerve plexus ablation) or implanted peripheral nerve stimulator which has affected bladder function.
383	10.	A history of a bladder calculus.
384	11.	A history of tuberculous cystitis.
385	12.	A history of neurologic disease or diabetic cystopathy.
386	13.	A history of malignant bladder tumors.
387	14.	A history of urethral cancer.
388 389	15.	Reports a urinary void with a maximum volume > 350 cc, as measured by a 24 hour-voiding diary.
390	16.	Currently has an active urethral calculus.
391	17.	Currently has a ureteral calculus.
392	18.	Symptomatic urethral diverticulum.
393 394	19.	Has an LFT $> 1.5$ times the respective institution's upper limits of normal at the Baseline 1 screening visit.
395	20.	Has abnormal blood coagualation tests results: PT or PTT (aPTT).
396	21.	Has platelet test results outside the respective institution's normal range.
397	22.	Reports any allergies to Elmiron ® or hydroxyzine.
398	23.	Currently taking cimetidine or currently on intravesical heparin.
399 400	24.	Chronic use (more than 3 out of 7 days each week) of greater than one gram of acetylsalicylic acid (e.g. aspirin, Bayer ® , Anacin ® , Excedrin ® , etc.).
401 402	25.	Chronic use (more than 3 out of 7 days each week) of aspirin replacement products (acetaminophen, NSAIDs, etc.) of more than the amount of milligrams in the

403 404		maximum single dose allowed by the Physicians' Desk Reference for prescription use, spread out over 24 hours.
405 406 407	26.	Chronic use (more than 3 out of 7 days each week) of sedating histamine-1 receptor antagonists (only those containing diphenhydramine, brompheniramine, or chlorpheniramine).
408	Exclusio	on criteria for men only:
409	27.	Having a residual urine volume >150 cc by ultrasound or catheter.
410 411 412	28.	Having had a TURP, TUIP, TUIBN, TUMT, TUNA, balloon dilation of the prostate, open prostatectomy or any other prostate surgery or treatment such as cryotherapy or thermal therapy.
413 414	29.	Currently being treated for chronic bacterial prostatitis as documented by a positive urine culture.

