640 641 642 643 644 645 646		Although all participants are expected to develop some initial adverse experiences from this medication, predominately sedation, it has been shown that participants tend to become tolerant to these effects if a slow titration is used (48). In addition, the entire dose of hydroxyzine will be given as one or two capsules before bedtime to minimize sedation effects during waking hours the following day.

647 648 649 650 651 652 653 654 655 656 657 658 659 660 661 662 663 664 665 666 667 668 669 670 671 672	
 
Participants will be instructed to increase their dose at the beginning of each new week during the dose stabilization phase (weeks 1-3) of the follow-up period, if they are not experiencing adverse experiences. The titration upward will be stopped if the participant reports that the adverse experiences are unacceptable. The dose of the study drug will then be reduced to the previously tolerated next lower dose for the remainder of that week. A second attempt to increase the dose by one step will be attempted. If this produces unacceptable adverse experiences, the dose will be lowered to the next lower level and maintained for the duration of the remaining weeks of follow-up. If the participant tolerates the higher dose, doses will be increased a step every week up to a maximum of 50 mg. The titration will be governed by the following rules:
 
Participants will be encouraged to take the highest dose of medication tolerated.
 
If a participant reports mild to moderate sedation at a particular dose, s/he will be kept on that dose for an extra week before restarting titration.
 
If the participant reports severe adverse experiences, they will be encouraged to reduce their dose by one level, but continue on the medication.
 
If there are adverse experiences and there is adequate time, participants will be encouraged to try a higher dose.
 
All doses should be stabilized by the end of 3 weeks.
 

673	8.3.2 Drug manufacturing and packaging
674 675	Hydroxyzine will be purchased from a certified supplier by the drug packaging and distribution center. An adequate supply of 10mg and 25 mg capsules will
676	be purchased, and over-encapsulated into green "look alike" capsules containing
677	either 10 mg (Dose 1), 25 mg (Dose 2), of hydroxyzine. These green capsules,
678	almost identical in size to the Elmiron capsules, will be packaged into blister

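### Section 8.3.1 gives opposite directions for the hydroxyzine dose step when a participant has adverse experiences

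*Protocol*

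**What the plan says.** Section 8.3.1 sets three daily dose steps: 10 mg in week 1, 25 mg in week 2 and 50 mg in week 3. The maximal tolerable dose chosen by the end of week 3 becomes the maintenance dose for the remaining 21 weeks.

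The running text allows the weekly step up "if they are not experiencing adverse experiences". It adds: "The titration upward will be stopped if the participant reports that the adverse experiences are unacceptable". The dose then returns to the last tolerated level for the rest of that week, after which "A second attempt to increase the dose by one step will be attempted". If that attempt fails, the lower dose is kept.

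A list of governing rules follows:

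- Participants are to be encouraged towards the highest dose they tolerate.
- For mild to moderate sedation, "s/he will be kept on that dose for an extra week before restarting titration".
- For severe experiences, the advice is to drop one level while staying on the drug.
- The fourth rule reads: "If there are adverse experiences and there is adequate time, participants will be encouraged to try a higher dose".
- Doses are to be settled within 3 weeks.

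The same section says: "Although all participants are expected to develop some initial adverse experiences from this medication, predominately sedation". That sentence goes on to say that tolerance tends to develop under slow titration.

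Section 8 gives its own instructions. Participants start week 2 on Dose 2 and step back, with the Research Coordinator's approval, if they cannot tolerate it. Those who complete week 2 on Dose 2 add Dose 3 in week 3. If Dose 3 is not tolerated, they go back to Dose 2 for two days and then try again.

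**The concern.** The running text and the fourth listed rule point in opposite directions for the same participant at the same decision. The situation is not remote, since some initial adverse experiences are expected in everyone on the drug. A coordinator at any of the eight clinical sites, speaking to a participant at the end of week 1 or 2, can find a sentence in 8.3.1 that supports holding the dose, reducing it or encouraging an increase.

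Two things are at stake. The first is safety: as printed, the fourth rule encourages a higher dose in participants whom adjacent rules hold, reduce or stop. The second is interpretation. Safety and tolerability, including drop-out, is the second primary objective, and withdrawals count as failures on the primary endpoint (Section 7.1). If sites titrate differently because they follow different sentences, the tolerability and drop-out results partly reflect site interpretation.

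**Working it through.** There is no stated figure to reproduce. The check is a comparison of sentences, followed by a dose path traced by hand.

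**Step 1. What each sentence directs, by grade of adverse experience**

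| Participant's state | Other sentences of 8.3.1 | Fourth listed rule |
|---|---|---|
| None | Step up at the new week | Not triggered |
| Mild to moderate sedation | Running text: condition for the step not met. List: one extra week at the same dose, then titration restarts | Encourage a higher dose |
| Severe | Running text: condition not met. List: encourage one level down, stay on drug | Encourage a higher dose |
| Unacceptable to the participant | Upward titration stops; back to the last tolerated dose; one second attempt | Encourage a higher dose |

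The fourth rule's only qualifier is that time be adequate. It does not mention severity, a prior reduction or the second attempt. In every row where it is triggered, it departs from at least one other sentence.

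**Step 2. Dose path for one illustrative participant**

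Inputs: steps of 10, 25 and 50 mg and a three-week window (Section 8.3.1). Assumptions: mild sedation begins on 10 mg in week 1 and persists; nothing severe or unacceptable occurs; the extra-week hold is applied once before titration restarts; time is judged adequate; and encouragement to step up is accepted.

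| Sentence followed | Week 1 | Week 2 | Week 3 |
|---|---|---|---|
| Running-text condition alone | 10 mg | 10 mg | 10 mg |
| Extra-week rule | 10 mg | 10 mg | 25 mg |
| Fourth listed rule | 10 mg | 25 mg | 50 mg |
| Section 8 card instructions, each step tolerated | 10 mg | 25 mg | 50 mg |

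The spread between the extremes is 50/10 = 5-fold. Even without the fourth rule, the running text and the extra-week rule differ by 25/10 = 2.5-fold for this participant.

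**Step 3. How long the difference lasts**

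The week-3 dose is carried for 24 − 3 = 21 weeks, which is 21/24 = 87.5% of follow-up. Section 8 allows one approved de-escalation on request in that period.

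**Step 4. Who could be affected**

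The rules apply, masked, to green capsules in all four arms. The milligram dose differs only in the two hydroxyzine arms, where 2 × 34 = 68 participants are planned. That is an upper bound. The protocol does not say how many would have sedation that persists to the next step.

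**The case against.** The strongest reply is that the fourth rule is a loosely worded re-challenge rule. The running text provides for a second attempt after a reduction, Section 8 describes stepping back and trying again, and a reference to adequate time fits a re-attempt inside three weeks. A dropped word is also possible. Both explanations are plausible, but the text states neither, and under either one the printed rule needs correcting.

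A second reply is that safeguards exist. The rule only encourages. The coordinator calls at the end of weeks 1 and 2 and must approve dose changes, unacceptable experiences stop the titration, and a failed second attempt fixes the lower dose. These limit the harm, but they do not tell the coordinator which sentence to apply.

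A third reply concerns the trial comparison. Doses vary by design, randomization is stratified by site, the primary test adjusts for center, and treatment is masked. This stands: differing site habits would vary the achieved dose and might dilute an effect, but they would not confound the comparison of arms.

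A reader might also infer two stronger points that the documents do not support:

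- **Nobody on active drug would leave 10 mg, so 0% would reach 50 mg.** This would follow only if sedation persisted in everyone. The expected experiences are described as initial, the condition is applied afresh at each new week, tolerance is expected, Section 12.1 says drowsiness usually passes within days, and the extra-week rule restarts titration.
- **10 mg does not count as treatment**, because exclusion criterion 6 (Section 5.4) refers to "greater than 10 mg of hydroxyzine per day for greater than 12 consecutive weeks". Deferral criterion 6 (Section 5.5) covers any hydroxyzine treatment without a dose threshold, so the comparison fails.

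**Conclusion.** Section 8.3.1 contradicts itself on the direction of the hydroxyzine dose step when adverse experiences are present, and the fourth listed rule as printed also conflicts with the adjacent hold, reduce and stop rules. This rests on the wording alone.

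The size is shown by one illustrative case: with persisting mild sedation on 10 mg, the dose carried into maintenance is 10, 25 or 50 mg according to the sentence followed. That case depends on the assumptions listed with the dose path and is not the course the protocol expects. The consequences are site-dependent titration and a participant-safety ambiguity bearing on the tolerability objective. No effect on sample size, significance level, power or response rate is shown or claimed, nor is any proportion of participants failing to reach the target dose. No view is taken on which dosing rule is right.

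**What to change.** The sponsor should:

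1. Reconcile the sentences of 8.3.1, and the matching titration instructions in Section 8, so that each grade of adverse experience (none, mild to moderate sedation, severe, unacceptable) leads to one action only.
2. State whether the fourth listed rule is misworded or applies only to a re-attempt after a reduction, and reword it accordingly.
3. Carry the reconciled text into the Manual of Procedures and the site and participant instructions.

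The clinical choice at each grade belongs to the sponsor. The cost is a wording amendment to two linked sections and the corresponding instructions, with the IRB notification that Section 13.1 requires for protocol changes. No extra visits, data or participants are needed.

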#### 688 8.4 Placebo for hydroxyzine 689 8.4.1 Dosing schedule 690 The placebo capsules will be manufactured to appear identical to over-691 encapsulated capsules of hydroxyzine and will be taken on the same schedule of 692 one or two capsules per day, at bedtime. 693 8.4.2 Placebo manufacturing and packaging 694 A matching placebo (identical green capsules containing microcrystalline 695 cellulose powder only) for hydroxyzine will be manufactured centrally in one 696 complete batch by the drug packaging and distribution center. The entire 697 quantity of placebo capsules will be packaged into blister packs, with the same 698 sequence for weeks 1, 2 and 3, for the titration period. Hydroxyzine placebo will be packaged in sealed bottles for the maintenance phase of the trial with the 699 700 participant's five-digit randomization number on the label.

# 701 9 Concomitant Medications

Hydroxyzine should be used with caution because of increased sedation when administered
together with central nervous system depressants, such as narcotics, non-narcotic analgesics,
barbiturates, benzodiazepines and sedating antihistamines. Anti-cholinergics should also be used
with caution because hydroxyzine may increase their anticholinergic effect and induce retention.
Finally, hydroxyzine should preferably not be used with medications that inhibit the ability of the
liver to metabolize drugs such as cimetidine as the serum concentration of hydroxyzine will be
increased because it, too, is metabolized by the liver.

Figure 2008 Figur

# 711 9.1 Excluded Medications

- 712 Participants will be excluded from this clinical trial if they are on the histamine-2 receptor
- antagonist cimetidine (e.g. Tagamet) at the time of screening. Participants will be withdrawnfrom the study if they initiate cimetidine usage.
- 715 Participants will be excluded from this clinical trial if they are on intravesical heparin.
- 716 Participants will be withdrawn from the study if they initiate intravesical treatment.
- 717 Participants will also be excluded if they report chronic use (more than 3 out of 7 days per week)
- 718 at the time of screening, of greater than one gram of acetylsalicylic acid (e.g. aspirin Bayer®,
- 719 Anacin®, Excedrin®, etc.). In addition, participants will also be excluded if they report chronic
- vise (more than 3 out of 7 days per week) at the time of screening, of aspirin replacement
- 721 products (e.g. NSAIDs, acetaminophen, ibuprofen, Motrin®, Advil®) of more than the amount of
- milligrams in the maximum single dose allowed by the Physicians' Desk Reference for
   prescription use, within a 24 hour period.
- 724 In addition, participants will be excluded from enrollment in this clinical trial, if at baseline
- screening visit 2 they report chronic use (more than 3 out of 7 days per week) of sedating

histamine-1 receptor antagonists (only those containing diphenhydramine, brompheniramine, orchlorpheniramine) (Appendix F).

728

# 729 10 RCT Tests, Procedures and Participant Withdrawal

730 10.1 Procedural Summary

[figure not shown]
This RCT will utilize a 2 x 2 factorial design to evaluate the effectiveness of 1) placebo
plus placebo, 2) placebo plus Elmiron® 3) hydroxyzine plus placebo 4) hydroxyzine plus
Elmiron® in the improvement of moderate to severe symptoms of pain/discomfort and
frequency in IC participants. Approximately 136 participants with clinically diagnosed
moderate to severe IC will be recruited from eight clinical sites throughout the United
States.

Prior to baseline screening, potential participants must have been diagnosed with IC, confirmed sometime in the past with the results from a cystoscopy/hydrodistention.

739 This study is comprised of two distinct phases for each participant: i) the screening 740 phase and ii) the treatment and follow-up phase (Appendix G). The screening phase, 741 which assesses a participant's eligibility via inclusion, exclusion and deferral criteria, will 742 consist of two "baseline" visits no more than 4 weeks and no less than 7 days apart. Any 743 candidate failing any of the inclusion or exclusion criteria will be considered ineligible 744 for the protocol and treated according to usual clinical care. Some participants who 745 initially fail study entry criteria may later be reconsidered for inclusion if the 746 exclusionary conditions resolve (section 5.3-5.5). Any participant meeting all of the 747 criterion will then be eligible for randomization to one of the four treatment arms. After 748 randomization, participants are asked to return to the clinic for follow-up visits at weeks 749 3, 10, 17 and 24. Study medications will be dispensed at each clinic visit and participants 750 will be asked to complete several quality of life and symptom scale questionnaires. At 751 week 24, any participant requesting to continue on study medication will be provided 752 masked medication until the study is closed. These participants will be followed every 753 12 weeks.

- 754 755 756
- 757
- 758
- 759
- 700
- 760
- 761
- 762
- 763

#### Figure 2. Treatment Design Schema

- 794 be instructed to remember his/her overall urinary symptoms on this day. He/she will be informed, that upon completion of the study, or withdrawal, whichever 795 comes first, he/she will be asked to compare the overall symptoms experienced 796 797 at Baseline Visit 2 to that at week 24. This visit must occur no less than 1 week 798 and no more than 4 weeks after the first baseline visit. In order to meet 799 eligibility criteria, the participant must report a voiding frequency of at least 11 800 times in a 24 hour day, and a pain/discomfort score of at least 4 at both Baseline 801 1 and Baseline 2 Visits (see all inclusion/exclusion/deferral criteria in Sections 802 5.3 to 5.5).
- 803If it is determined that the participant meets all eligibility criteria, then804randomization to one of the four treatment arms is implemented. Participants805will be stratified by randomization site and randomized in equal proportions to806one of the four treatment arms, using a randomized block design with varying807block sizes.
- 808 At the time of randomization, the participant will be provided with both study medications and thorough instructions on how to take each of them. The RC 809 810 must approve and document any changes in study medication dosages during the 3 week titration/dose stabilization for the green capsules. The following 811 questionnaires will also be administered: Symptom Ranking Cards, IC 812 Symptom & Problem Index, University of Wisconsin Symptom Survey, Health 813 Status Questionnaire (MOS SF-36), and the MOS Sexual Functioning Scale. In 814 addition, a urine sample will be collected, processed, frozen and shipped to the 815 Core Pathology Laboratory, for storage (Appendix H). In addition, the 816 817 participant will be asked to maintain a daily medication diary. This diary will be returned and replaced with another booklet at every clinic visit. 818

#### 10.1.3 Treatment and Follow-up

819

820

821

822 823

824

825 826

827

828

Participants will return for follow-up visits at week 3 and every seven weeks following (Appendix G). At weeks 3, 10, 17, and 24 participants will complete the IC Symptom & Problem Index, the University of Wisconsin Symptom Survey, the Follow-up Symptoms form, and return the Voiding Diary and Daily Medication Diaries. The participants will receive a telephone call from the RC at weeks 1, 2, 3, 6, 14, and 20. At each scheduled contact, they will be asked about excluded/restricted medications, any possible adverse events, and initiation of IC treatments. In addition, study medication compliance will be calculated at weeks 10, 17 and 24.

829At the final clinic visit on week 24, participants will be asked to complete the830Symptom Ranking Cards, the Health Status Questionnaire (MOS SF-36), the831MOS Sexual Functioning Scale, the Patient Close-out Form, and undergo a832physical examination. Urine samples will be collected, processed, frozen and833shipped to the Core Pathology Laboratory for storage. In addition, at week 24,834LFTs, the blood-coagulation tests and platelet test will be performed (Appendix835G).

836		10.1.4 Post Treatment Period
837 838 839 840 841 842 843		Any participant requesting to continue on study medication will be provided masked study medication until the study is closed to all accrual and follow-up visits. Every 12 weeks, these participants will be asked the Follow-up Symptoms measure, IC Symptom Problem Index, University of Wisconsin Symptom Survey, and return the Voiding Diary. Adverse events, serious adverse events, addition of excluded/restricted medications or IC treatments will also be recorded.
844		10.1.5 Participant Withdrawal
845 846 847 848 849 850 851 852 853 854 855 856 857		Under certain circumstances, a study participant may have his/her treatment terminated prior to the 24 week clinic visit. These circumstances include: unacceptable concomitant medications/treatments (e.g. cimetidine, or intravesical heparin), a positive pregnancy test, and unacceptable adverse events as determined by the Principal Investigator (P.I.). In addition, if a participant has 2 consecutive abnormal LFT tests ( $2.5 X$ 's > than the respective institution's upper limits of normal) or 2 consecutive abnormal blood coagulation test results post randomization, the subject will be withdrawn. In addition, any participant who acquired a serious or life-threatening medical condition while participating in the study may have the study treatment terminated early at the discretion of the P.I. Participation in the study may also be terminated early as a result of participant dissatisfaction with treatment or participant disinterest in continued study participation.
858 859		A participant may also undergo early study termination because of a change of residence outside the driving distance of the ICCTG network.
860	10.2	Clinical and Laboratory Procedures
861		10.2.1 History and Physical Examination
862 863 864 865		Each participant will undergo a physical examination including height, weight and blood pressure. For females, the physical examination will include a bimanual exam and external genital exam. For males, this examination will include an external genital exam and rectal exam.
866		10.2.2 Urine Sample
867 868 869 870 871 872 873 874		Two urine samples will be obtained for the purpose of maintaining a study specimen bank containing urine collected from all participants at the Baseline 2 Visit and the week 24 visit. The urine specimens will be collected, processed, and frozen at the study site at $-70^{\circ}$ C. Periodically, the frozen urines will be shipped in batches to the Core Pathology Laboratory for central storage and future research investigating selected biomarkers. Details of procedures for urine collection, processing, and shipping are given in Appendix H.
875 876		Elevated levels of three markers of bladder mast cell activity have been found in IC urine specimens: methylhistamine, tryptase and IL-6. Methylhistamine is

877	the major metabolite of histamine which is released by activated mast cells.
878	Although histamine levels were only slightly increased in spot urine specimens
879	from IC patients, methylhistamine levels were shown to be greatly elevated,
880	suggesting that they may serve as an important marker of disease activity.
881	Tryptase is a proteolytic enzyme also released by activated mast cells; unlike
882	methylhistamine which can be excreted intact into the urine, urine tryptase is
883	thought to be specific for urinary tract pathology, and elevations in urine
884	tryptase in IC patient specimens were therefore taken as evidence of increased
885	urinary tract mast cell activity. However, the measurement of tryptase by itself
886	is not as sensitive of a marker for IC as is methylhistamine, making it desirable
887	to measure both substances. IL-6 is a cytokine which has also been shown to be
888	elevated in the urine of IC patients, and which can be elevated in the absence of
889	detectable mast cell degranulation. The measurement of all 3 substances should
890	therefore provide a very sensitive indication of bladder mast cell activity.
891	
892	Another marker for IC has been described which appears to be very specific and
893	sensitive for the disease itself - a urine "antiproliferative factor" or "APF". This
894	factor is a low molecular weight peptide that inhibits the proliferation of
895	primary normal human bladder epithelial cells in vitro. Because the bladder
896	epithelium is abnormally attenuated in this disease, it is thought that the APF
897	may be causally related to the disease process. Levels of this factor by IC
898	patients have recently been shown to be decreased following bladder
899	hydrodistension, a treatment currently used for IC and beneficial in some
900	patients, making it another potential indicator of disease activity.
901	putonts, making it another potential indicator of discuse activity.
902	Because the primary parameters to be measured for this study are subjective in
903	nature, potential objective measurements of disease activity were thought to be
904	desirable. It is thought that the first 3 markers (methylhistamine, tryptase, and
905	IL-6) may serve as objective indicators of whether the antihistamine in this
906	study has an effect on bladder mast cell activity, and the fourth marker (APF)
907	may serve as an objective indicator of whether the antihistamine and/or Elmiron
908	have a measurable effect on another aspect of the disease process.
	have a measurable effect on another aspect of the disease process.
909	
910	10.2.3 Urinalysis and Culture and Other Urine Tests
911	The urinalysis and culture is useful in the evaluation of renal, urinary, and
912	metabolic disorders. A chem-strip 9 will be used. The parameters that will be
913	assessed are Nitrite, Blood, Hemoglobin, Leukocytes, and Urine Culture. A
914	residual urine volume test will be performed on men via ultrasound or catheter.
915	10.2.4 Blood Draw Procedures
916	A serum pregnancy test will be performed on all women at risk for pregnancy
917	(still menstruating). If the test is positive, the subject will be excluded. In
918	addition, Liver Function Tests (LFTs) (AST, ALT, Glutamyltransferase, and
919	Alkaline Phosphatase), blood coagulation tests (PT and PTT) and platelet test
920	will be performed at Baseline 1, and week 24.

921	If either the LFTs or blood coagulation tests are abnormal on two separate
922	occassions post randomization, the participant will be withdrawn from the
923	study.

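### The laboratory withdrawal rule needs two abnormal post-randomization results but only one post-randomization test is scheduled, and sections 10.1.5 and 10.2.4 word the rule differently

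*Protocol*

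**What the plan says.** **Schedule.** Section 10.2.4 states that LFTs, PT/PTT and the platelet test "will be performed at Baseline 1, and week 24". Section 10.1.3 also places them at the final clinic visit: at week 24 the LFTs, "the blood-coagulation tests and platelet test will be performed", with a reference to Appendix G. Section 10.1 sets the follow-up visits at weeks "3, 10, 17 and 24. Study medications will be dispensed at each clinic visit and participants" complete questionnaires. No blood test is stated for weeks 3, 10 or 17.

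**Extension.** Participants who ask to may stay on masked medication after week 24, with contact every 12 weeks. Section 10.1.4 says that "these participants will be asked the Follow-up Symptoms measure, IC Symptom Problem Index, University of Wisconsin Symptom Survey, and return the Voiding Diary". Adverse events and added medications are also recorded. No LFT or coagulation test is listed.

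**Rule, section 10.1.5.** This section deals with treatment ended before the week 24 visit. Withdrawal follows "if a participant has 2 consecutive abnormal LFT tests" at 2.5 times a limit, worded as "than the respective institution's upper limits of normal) or 2 consecutive abnormal blood coagulation test results post randomization, the subject will be withdrawn".

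**Rule, section 10.2.4.** "If either the LFTs or blood coagulation tests are abnormal on two separate" occasions after randomization, the participant is withdrawn from the study. This version gives no multiple of the ULN and does not ask for consecutive results.

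**The concern.** A mandatory withdrawal rule should be able to act on the data that the protocol collects. Here the rule counts two post-randomization results and the schedule supplies one, at the end of the 24 weeks. Safety and tolerability is a stated primary objective (sections 2 and 15.2), and section 12.1 lists liver function abnormalities among the known Elmiron events.

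The two wordings raise a separate problem. Sections 7.1 and 15.2 count anyone who withdraws from the study before the week 24 assessment as a treatment failure. If unscheduled tests bring the rule into play, the section that a site follows can decide whether a participant is withdrawn, and so how that participant counts in the primary response rate.

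**Working it through.** The protocol gives no figure to reproduce. The check is a count, followed by a comparison of the two rule texts.

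**Step 1: scheduled tests against results needed**

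| Period | Scheduled LFT/coagulation tests | Source |
|---|---|---|
| Before randomization | 1 (Baseline 1) | 10.2.4 |
| Weeks 1 to 23 | 0 | 10.1, 10.1.3, 10.2.4 |
| Week 24 | 1 | 10.1.3, 10.2.4 |
| 12-weekly extension | 0 listed | 10.1.4 |

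Scheduled post-randomization results: 0 + 1 + 0 = 1. Abnormal results needed under either version: 2. Shortfall: 2 − 1 = 1. Before week 24, the period that section 10.1.5 addresses, the count is 0 against 2.

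**Step 2: can Baseline 1 supply one of the two?** No. Section 10.2.4 restricts both kinds of test to occasions after randomization. In section 10.1.5 the same restriction could be read as attached only to the coagulation tests. Even on that reading, exclusion criterion 19 bars any LFT above 1.5 times ULN at Baseline 1, so an enrolled participant cannot bring in a value at 2.5 times ULN. Exclusion criterion 20 bars abnormal PT or PTT.

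**Step 3: the two versions side by side**

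| | 10.1.5 | 10.2.4 |
|---|---|---|
| LFT level | 2.5 × ULN | abnormal, no multiple |
| Coagulation level | abnormal | abnormal |
| Pattern | 2 consecutive | 2 separate occasions |

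Suppose a participant has two unscheduled LFTs at 2.0 × ULN before week 24. Section 10.2.4, read literally, requires withdrawal, and the participant becomes a treatment failure. Under section 10.1.5, 2.0 is below 2.5, so the rule does not apply; the participant stays and can still be a responder. Two abnormal coagulation results with a normal one between them split the sections in the same way. Read literally, section 10.2.4 could also cover LFTs between 1.0 and 1.5 × ULN, which exclusion criterion 19 accepts at entry.

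**Step 4: scale**

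- Elmiron-exposed participants: 2 arms × 34 = 68. Section 12.1 gives 1% to 4% for its listed events: 68 × 0.01 = 0.68 and 68 × 0.04 = 2.72, so about 0.7 to 2.7 participants with a liver function abnormality. The protocol does not say how many would reach 2.5 × ULN, or do so twice.
- Section 15.3 expects up to 30% to withdraw before the final assessment: 136 × 0.30 = 40.8. About 41 is therefore an upper bound on those who, by not attending week 24, would have no scheduled post-baseline laboratory result.

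**The case against.** The strongest reply is that the rule speaks of results after randomization, not of scheduled results. A rule based on two results is naturally read as confirmation by repeat test, including tests prompted by an adverse event. That stands as far as it goes: unscheduled tests could satisfy the rule. But the text provides for no repeat test and sets no trigger or timing for one.

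A reader might infer that participants have no working laboratory or liver protection during treatment. The protocol does not support that. The investigator may end treatment for unacceptable adverse events or a serious condition (10.1.5). Adverse events are asked about at every scheduled contact, including calls at weeks 1, 2, 3, 6, 14 and 20 (10.1.3). A clinically significant laboratory abnormality can itself be an adverse event (12.1).

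A reader might also infer that the laboratory summary will describe completers only, with 30% missing. That goes too far: 30% is a maximum for withdrawal before the response assessment, and section 15.3 encourages those who stop treatment to stay in follow-up, so some would still have week 24 blood tests.

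Nor are there two competing thresholds. One section gives a multiple for LFTs and the other gives none, so the shorter text may be meant as shorthand. The difference between consecutive and separate occasions remains, and for coagulation it is the only difference.

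Finally, the content of Appendix G is not in the text at hand and may list further draws. If it does, it would contradict sections 10.1.3 and 10.2.4, and reconciliation would still be needed.

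**Conclusion.** The point holds as a contradiction within the protocol. On scheduled testing there is one post-randomization result in the 24 weeks against two required, and none before week 24. The rule can be met only through unscheduled or repeat tests that the text does not describe. Week 24 is not the last on-drug visit for those who continue masked medication, but no laboratory test is listed for them afterwards, so the extension does not supply the second result either.

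The two versions can classify the same participant differently. This reaches the primary endpoint only when two qualifying results arise before the week 24 assessment, and both would then be unscheduled. The number affected cannot be derived from the protocol and is probably small. The sample size, the significance level and the primary test are untouched. The consequence lies with the primary safety objective and with consistent handling across sites.

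The conclusion assumes that sections 10.1.3, 10.1.4 and 10.2.4 state the full laboratory schedule. If Appendix G adds draws, the mismatch becomes one between text and table.

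**What to change.** Reconcile sections 10.1.3, 10.1.4, 10.1.5 and 10.2.4 with Appendix G, so that:

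- the test time points, including any repeat tests the rule relies on, can supply the number of results that the rule counts while participants are on study drug, and the position during the extension is explicit;
- the withdrawal rule appears in identical words wherever it is stated, covering the LFT level, what counts as abnormal for coagulation, and whether the results must be consecutive.

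Which schedule and which threshold to adopt is the sponsor's clinical decision, and this review takes no position on it. The cost is a protocol amendment: text only if the schedule is unchanged, or added blood tests at visits that already take place if it is not. It is best done before enrolment, so that all sites apply one rule.
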